## PROTOCOL SUMMARY

**Overall rationale:** Prophylactic NAC irradiation after nipple-areola sparing mastectomy and immediate reconstruction for patient with ductal carcinoma in-situ or invasive breast cancer will allow better cosmesis and patient's satisfaction.

**Study design:** Phase I trial assessing the safety, feasibility and toxicity of prophylactic NAC irradiation after nipple-areola sparing mastectomy and immediate reconstruction in patients with ductal carcinoma in-situ or invasive breast cancer.

**Primary objective:** To determine the recommended phase I dose of post-operative prophylactic NAC irradiation.

**Secondary objectives:** To provide extensive descriptive data regarding NAC-sparing surgery with reconstruction, including both surgeon experience and patient evaluation of cosmetic results. Survival and recurrence will be assessed.

**Study size:** Between 12 and 18 patients will be enrolled in the dose-escalation/de-escalation part of this phase I study. An additional **expansion cohort of 12 patients** will be enrolled at the “**potential” recommended phase II dose (RP2D)** over an expected accrual period of 2 years.

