**Dose level II: 25 Gy total (2.5 Gy for 10 fractions) (Starting Dose)**

Dose level III: 30 Gy total (3.0 Gy for 10 fractions)

Dose level IV: 35 Gy total (3.5 Gy for 10 fractions)

The patients will be receiving postoperative NAC irradiation using electrons **starting at Dose level II**. Dose levels will be escalated by 0.5 Gy per fraction for an overall 5 Gy increase per level up to 3.5 Gy per fraction and a total dose of 35 Gy. **Evaluable patients** will be defined as any eligible patient that begins NAC irradiation treatment.

DLT (dose-limiting toxicity), as defined in section 4.2.6, will be evaluated during radiation treatment period plus an **additional observation period of 30 days** following completion of NAC radiation.

We propose a **modification of standard dose-escalation design, treating cohorts of 2 to 6 patients per dose level of NAC irradiation**. The main features of the proposed escalation design is that (1) no more than 2 patients will experience DLT at a given radiation dose and (2) escalation to a higher dose occurs only after a cohort of 6 patients have been evaluated at a given radiation dose.

Dose escalation/de-escalation rules	
Number of patients with DLT at a given dose level	Escalation Decision Rule
0 or 1 out of 6 patients	Enter 6 patients at the next higher dose level.
2 out of 2 to 6 patients	Dose escalation stops. However, if the dose tested is dose level II, the starting dose level, then de-escalation occurs. In this case, dose level I will be tested in 2 to 6 patients.
The highest dose tested at which $\leq 1$ out of 6 patients experiences DLT will be declared the MTD and it will be the recommended phase II dose .	

Thus, as stated in the dose escalation/de-escalation rules above, if 0 or 1 patient experiences DLT (as defined in section 4.2.6) among 6 patients, the dose level will be judged to be acceptable. If this occurs, then a new cohort of 2 to 6 patients will be accrued at the next higher dose level. If 2 patients experience DLT among 2 to 6 patients at a given dose level, then the corresponding dose will be declared to be unacceptable. If the **starting dose level** (dose level II) proves to be unacceptable, then de-escalation occurs to dose level I and 2 to 6 patients will be enrolled at dose level I.

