## 10.0 STATISTICAL CONSIDERATIONS

### 10.1 Study Size

For the purpose of dose escalation of NAC-radiation treatment, **evaluable patients** will be defined as any eligible patient that begins NAC irradiation treatment. However to evaluate feasibility of the NAC-sparing mastectomy with reconstruction, any patient who undergo surgery will be considered evaluable.

Following the dose escalation/de-escalation procedure described in section 4.2, we anticipate that 12 to 18 evaluable patients will be enrolled in this phase I study *during the dose-finding part*. The **number of evaluable patients** that will be needed depends on the number of times the NAC-radiation dose is escalated or possibly de-escalated. If the escalation occurs from dose level II up to dose level IV, between 14-18 evaluable patients will be required. If the dose is de-escalated after dose level II been evaluated in 6 patients, then 12 evaluable patients will be required, assuming 6 patients would be evaluated at dose level I. With 6 evaluable patients, the probability of not escalating when the true DLT rate is 35% is 68%. If the true DLT rate is 20%, the probability that the dose will be escalated is 66%.

A maximum of 6 patients per year is expected to be enrolled, since each patient must be evaluated for a minimum of 35 days and at most two patients will be enrolled simultaneously (within < 30 days after completion of the 5 days NAC radiation treatment). Thus, the expected accrual period is between 2-3 years.

An **additional expansion cohort of 12 patients** will be enrolled at the “**potential**” **recommended phase II dose (RP2D)** over an expected accrual period of 2 years.

To gather data on recurrence and survival, all patients will be followed at their clinic visits as clinically indicated.

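### The stated dose-finding size of 12 to 18 has the wrong lower limit: the 4.2.5 rules give 8 to 18 evaluable patients when an MTD is found, and 4 to 12 when none is

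*Combined protocol and SAP*

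**What the plan says.** The Study size entry of the Protocol Summary reads "Between 12 and 18 patients will be enrolled in the dose-escalation/de-escalation part of this phase I study". Section 10.1 is softer: "we anticipate that 12 to 18 evaluable patients will be enrolled in this phase I study". It counts evaluable patients, where an evaluable patient "will be defined as any eligible patient that begins NAC irradiation treatment".

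Section 10.1 supports the range with two sub-totals. For escalation to the top dose: "If the escalation occurs from dose level II up to dose level IV, between 14-18 evaluable patients will be required". For de-escalation after level II has been evaluated in 6 patients: "then 12 evaluable patients will be required, assuming 6 patients would be evaluated at dose level I". It gives no total for a trial in which level II is acceptable and level III is not, and none for a trial in which levels II and I both fail.

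The rules are in Section 4.2.5, with the table repeated in the Summary. A level is acceptable with 0 or 1 DLT in 6 patients and unacceptable once 2 patients have a DLT among 2 to 6. A main design feature is that "no more than 2 patients will experience DLT at a given radiation dose". On the size of the next cohort, the table says "Enter 6 patients at the next higher dose level", while the text below it says "then a new cohort of 2 to 6 patients will be accrued at the next higher dose level".

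**The concern.** A level that fails need not use 6 patients. If it can close after 2, 3, 4 or 5, a trial that opens only two levels can finish with fewer than 12 evaluable patients, and 12 cannot be the lower limit. Section 10.1 also appears to count in two ways: 14 for the path to level IV is 6 + 6 + 2 and so allows a short last cohort, while 12 for de-escalation takes both levels as full.

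What is at stake is the description of the study. A reader of the Summary would take 12 as the fewest patients in the part of the trial that selects the dose, and 12 + 12 = 24 as the smallest study total once the 12-patient expansion cohort is added.

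**Working it through.** **Inputs (Sections 4.2.5 and 10.1).** Start at level II; one level lies below it and two above. A level passes with 0 or 1 DLT in 6 and closes at the second DLT, at patient 2 to 6. Simultaneous enrolment does not change the closing number: a pair is entered only while the level has no DLT, so a second DLT within that pair must be the pair's second patient.

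**The plan's own figures.** 6 + 6 = 12 (levels II and I both full); 6 + 6 + (2 to 6) = 14 to 18 (level IV reached). With 6 patients, P(escalate) at a 20% DLT rate is 0.8^6 + 6(0.2)(0.8^5) = 0.655, and P(not escalate) at 35% is 0.681. These match the 66% and 68% in 10.1, so the rules have been read as the plan intends.

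**All paths.**

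| Path | Evaluable patients | MTD |
|---|---|---|
| II passes, III stops | 6 + (2 to 6) = 8 to 12 | II |
| II stops, I passes | (2 to 6) + 6 = 8 to 12 | I |
| II and I both stop | (2 to 6) + (2 to 6) = 4 to 12 | none |
| II and III pass, IV stops | 6 + 6 + (2 to 6) = 14 to 18 | III |
| II, III and IV pass | 18 | IV |

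The 18 is reproduced. The 12 is the maximum of each of the first three rows.

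**How often.** For DLT rate p at a level, P(close at patient n) = (n − 1)p²(1 − p)^(n−2) for n = 2 to 6, and P(pass) = (1 − p)^6 + 6p(1 − p)^5. The plan gives no rates by level, so these are assumptions. Worked through at a flat 20%:

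- Close at 2 to 5: 0.0400 + 0.0640 + 0.0768 + 0.0819 = 0.2627. Close at 6: 0.0819. Pass: 0.6554.
- II passes, III closes before 6: 0.6554 × 0.2627 = 0.172.
- II closes before 6, I passes: 0.2627 × 0.6554 = 0.172.
- II and I both close, not both at 6: 0.3446² − 0.0819² = 0.112.
- P(fewer than 12) = 0.172 + 0.172 + 0.112 = 0.456, of which 0.344 is with an MTD found.

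| Assumed DLT rate, levels I to IV | P(fewer than 12) | P(fewer than 12 and MTD found) | Expected size |
|---|---|---|---|
| 5% flat | 4% | 4% | 17.5 |
| 10% flat | 16% | 14% | 16.2 |
| 5/10/20/35% | 31% | 31% | 14.0 |
| 20% flat | 46% | 34% | 13.2 |

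The extremes are uncommon in these scenarios: exactly 8 patients has probability 0.5% to 7.5%, and fewer than 8 has 0.02% to 3.3%. A flat 35%, the other rate that 10.1 uses, gives 82% below 12 (36.5% with an MTD), but it supposes that even 20 Gy causes a DLT in about one patient in three.

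**The case against.** The best defence is that 10.1 gives a planning figure. It is worded as an anticipation, says that the number depends on how often the dose is escalated or de-escalated, and prints its condition of 6 patients at level I. Under that condition, with level II also full, 12 is correct. This stands for 10.1 as an expectation. It does not cover the Summary's size statement, which carries neither hedge nor condition, and it does not explain why 10.1 allows a short cohort at level IV but not elsewhere.

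A second defence is the table's instruction to enter 6 at the next level. Taken as a fixed 6, every escalating path would total 12 or 18. That contradicts the 2-to-6 wording beneath the table and the 14 in 10.1, and it still leaves level II free to close early before de-escalation. Nor can closed levels be filled to 6 as a rule. Given 2 or more DLTs in 6, the chance of 3 or more is 14%, 29% and 52% at DLT rates of 10%, 20% and 35%, against the design feature limiting a dose to 2.

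A reader might infer more than the documents support:

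- *That the dose would rest on too little data, or that the design is unsafe.* Every MTD still needs 6 patients at that dose, and under 4.2.7 it is only a potential RP2D until safety is confirmed in 18. Totals below 12 arise because a toxic level closed early, which is what the rule is for.
- *That 20 to 30 is a firm study total once an MTD is found.* It holds only if all 12 expansion patients are treated. Section 10.3.2 suggests termination at 3 toxicities in 3 to 5 expansion patients, so 8 + 3 = 11 is possible; 10.3.3 has a similar guideline for surgical toxicity. Both are guidelines for the DSMC.
- *That the chance of fewer than 12 is also the chance of a study total below 24 when an MTD is found.* At a flat 20% the first is 45.6%; fewer than 12 jointly with an MTD is 34.4%, and given an MTD it is 39.1%.

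**Conclusion.** The lower limit of 12 is wrong as a statement of what the 4.2.5 rules deliver. The range is 8 to 18 evaluable patients when an MTD is found (13 cannot occur) and 4 to 12 when levels II and I are both unacceptable, barring earlier suspension under 10.3. These counts follow from the rules alone and need no assumed rates.

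The chance of falling below 12, 4% to 46% over the four scenarios tabulated, does rest on assumed DLT rates and on independence between patients. In those scenarios the expected size of 13.2 to 17.5 lies inside the stated range; at 6 patients a year that is 2.2 to 2.9 years, so the 2-to-3-year accrual estimate need not change. Maximum enrolment, the decision rules and the 68% and 66% probabilities are also unaffected. Severity is minor.

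**What to change.** In the Summary and in 10.1, state: *under the 4.2.5 rules, 8 to 18 evaluable patients if an MTD is found, and 4 to 12 if levels II and I are both unacceptable, barring earlier suspension under 10.3.* The Summary should say evaluable, because patients taken off study before irradiation make the number enrolled larger.

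In 10.1, add a total of 8 to 12 for a stop at level III, and change the de-escalation figure from 12 to 8 to 12 if level I is acceptable. Keep 14 to 18 for level IV. In the rule table, bring the entry for the next higher level into line with the 2-to-6 wording below it.

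If a study total is given, state 20 to 30 (8 + 12 to 18 + 12) only for a completed expansion cohort, with a note that 10.3.2 and 10.3.3 may end the study sooner.

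The cost is a few lines of text. The design, rules, maximum enrolment and accrual estimate stay as they are.

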### Treatment plan (07-15-2011)

Week 1	NAC-sparing mastectomy with immediate reconstruction
Between weeks 5 to 8	Prophylactic NAC irradiation twice daily, minimum of 4 hours apart, for 5 days , preferable in consecutive working days
2 weeks after irradiation	Chemotherapy, if indicated, at the discretion of the treating physician

### Dose escalation/de-escalation design (section 4.2) (07-15-2011)

Dose levels†	Description
Dose Level I = 20 Gy	10 fractions of 2.0 Gy
Dose Level II = 25 Gy (starting dose)	10 fractions of 2.5 Gy
Dose Level III = 30 Gy	10 fractions of 3 Gy
Dose Level IV = 35 Gy	10 fractions of 3.5 Gy

† Treatment will be delivered twice a day, minimum of 4 hours apart, **for 5 days**, preferable in consecutive working days.

The patients will be receiving postoperative NAC irradiation **starting at Dose level II**.

DLT (dose-limiting toxicity), as defined in section 4.2.6, will be evaluated during radiation treatment period plus an **additional observation period of 30 days** following completion of NAC radiation.

A **modification of standard dose-escalation design**, treating cohorts of 2 to 6 patients per dose level of NAC irradiation, will be used. The main features of the proposed escalation design is that (1) no more than 2 patients will experience DLT at a given radiation dose and (2) escalation to a higher dose occurs only after a cohort of 6 patients have been evaluated at a given radiation dose.

Dose escalation/de-escalation rules	
Number of patients with DLT at a given dose level	Escalation Decision Rule
0 or 1 out of 6 patients	Enter 6 patients at the next higher dose level.
2 out of 2 to 6 patients	Dose escalation stops. However, if the dose tested is dose level II, the starting dose level, then de-escalation occurs. In this case, dose level I will be tested in 2 to 6 patients.
The highest dose tested at which $\leq$ 1 out of 6 patients experiences DLT will be declared the MTD and it will be the recommended phase II dose .	

### **Expansion cohort (section 4.2.7)**

An additional **expansion cohort of 12 patients** will be enrolled at the “**potential recommended phase II dose (RP2D)** over an expected accrual period of 2 years.

**(See section 4.2 for further details.)**

## **HYPOTHESIS:**

- The use of NAC-sparing mastectomy followed by postoperative NAC (nipple-areola complex) external beam radiotherapy for selected patient with early stage invasive or in-situ breast cancers will be technically feasible and with acceptable complication rates.
- The cosmetic results after NAC-sparing mastectomy followed by postoperative external beam radiotherapy to the NAC will be better comparable with Skin Sparing Mastectomy.
- The local control rate in the NAC will be more than expected for a NAC sparing mastectomy without postoperative radiotherapy.
- The patient's satisfaction after NAC-sparing mastectomy followed by postoperative NAC external beam radiotherapy will be better than after Skin Sparing Mastectomy.

## **1.0 BACKGROUND**

### **1.1 NAC-sparing Mastectomy:**

Breast-conserving surgery is an option for the majority of patients with stage I/II invasive or noninvasive breast cancers. However, there are patients that require or elect to undergo mastectomy followed by a reconstruction. Skin-sparing mastectomy (SSM) has become a surgical option for an invasive or in-situ breast cancer requiring mastectomy or in high-risk patients undergoing prophylactic mastectomy. Several non-randomized series suggest that SSM does not add to the risk of local recurrence . The SSM removes the breast, nipple-areola complex (NAC), previous biopsy incisions and skin overlying superficial tumors. The preservation of the skin of the breast and inframmary fold with SSM, greatly improves the aesthetic results of the immediate breast reconstruction. The preservation of the nipple-areola complex (NAC) would lead to the best cosmetic result; however, the oncologic safety of lesser surgery is not yet proven. The incidence of occult involvement of the NAC in patients with established breast cancer has been reported in several published studies. Laronga and colleagues  reviewed a series of 286 mastectomy specimens at MD Anderson Cancer Center for the presence of occult NAC involvement. Occult tumor in the NAC was found in 5.6%. NSABP B-04 study (radical mastectomy versus total mastectomy ± radiation) noted the incidence of occult nipple involvement in 107 of 967 cases (11.1%) . Santini and colleagues  reported the largest series of NAC involvement. 1,291 consecutive mastectomy specimens with primary invasive breast cancer were reviewed, showing a 12% NAC involvement. Several published studies identified features of the primary breast cancer to increase risk of occult NAC involvement , including tumors < 2 cm from the areola, dimpling of the areola, tumors > 4 cm, multicentric tumors, location beneath the areola, presence of positive axillary nodes, presence of extensive intraductal component (EIC), etc.

Gerber and colleagues  published the largest series of NAC preservation, comparing the results of 112 patients undergoing SSM with preservation of NAC to 134 patients that had standard mastectomy. All tumors were > 2 cm from the nipple. After intra-operative frozen sections of the NAC-ground, they were able to preserve NAC in 61 patients (54.5%). There was no statistical difference in the rate of local recurrence with a follow up of 59 months. The subcutaneous mastectomy (SCM), which saves both the nipple and areola, has also been studied to treat established breast cancers and for risk-reduction operations. The number of studies using SCM in established breast cancer is small and appeared to show no difference in survival comparing from standard mastectomy, but with a higher incidence of local recurrence .

## **1.2 NAC-sparing Mastectomy followed by Prophylactic NAC Irradiation.**

Petit and colleagues  reported a prospective study using nipple-sparing mastectomy (NSM) in association with intra-operative radiotherapy with electrons (ELIOT) given to the NAC, in attempt to decrease risk of local recurrence and increase patient's satisfaction and cosmetics. Frozen sections of the tissue under the areola were routinely sampled to exclude presence of tumor. A dose of 16 Gy was delivered intra-operative in the region of the NAC. Between March 2002 and September 2003, 106 NSM were performed in 102 patients, 63% with invasive carcinoma and 37% in situ carcinoma. In an average follow up of 13 months, only one local recurrence, located in the clavicular region, far from the NAC was observed. 15 patients (4.7%) lost their NAC due to total necrosis. Eleven patients (10.4%) developed moist desquamation, followed by spontaneous healing. A preliminary result of a psychological part of the study showed a very high satisfaction with the preservation of the nipple (97.6%).

## **1.3 Radiation Dose and Fractionation:**

Several groups have recently published their data exploring the possibility of shortening the overall radiation treatment length after breast conserving surgery by increasing the fraction size, and decreasing treatment to the lumpectomy cavity with margins, where the majority of the recurrences occurred. 3D Conformal Radiation Therapy (3D-CRT) techniques have also been used in phase I/II trials. Formenti et al  published their experience treating 47 patients with early stage breast cancer after lumpectomy with 3D conformal partial breast irradiation. Patients received a total dose of 30 Gy at 6 Gy/fraction delivered in 5 fractions over ten days. At a median follow-up of 18 months, no patient developed a local recurrence, acute toxicity was modest (grade 1-2 erythema), with only grade 1 late toxicity. Baglan et al  also initiated a pilot study of 3D-CRT using doses of 34 Gy in 5 patients and 38.5 Gy in 4 patients, both delivered in 10 fractions, twice daily over 5 consecutive days. The acute toxicity was minimal. Radiobiological models suggest that this fractionation schedule of 38.5 Gy in 10 fractions using 3D-CRT external beam radiation should produce acceptable control rates in the breast and comparable late effects as with brachytherapy. These models estimate that the

regimen of 38.5 Gy in 10 fractions should provide a biologically equivalent dose (BED) of 45 Gy in 1.8 Gy fractions assuming a  $\alpha/\beta$  ratio of 10. The Radiation Therapy Oncology Group (RTOG) has launched a phase III trial (0413), comparing whole breast irradiation delivered over 6 ½ weeks versus partial breast irradiation in shortened treatment length of 5 days, using different techniques as MammoSite HDR brachytherapy (34 Gy, 3.4 Gy fraction, in 10 fractions, minimum of 6 hours apart), 3D-Conformal Radiotherapy (38.5 Gy in 10 fractions, twice daily, 6 hours apart) or Intertitial Brachytherapy with High or Low Dose Rate Brachytherapy.

The proposed study will evaluate the use of external beam radiotherapy using electrons, which is a superficial radiation, for treatment of the nipple-areola complex, postoperative. The dose escalation level IV of 35Gy in 3.5 Gy fractions, for a total of 10 fractions, twice daily, minimum of 4 to 6 hours apart, has a Biological Effective Dose (BED) equivalent of the standard fractionation of 45 Gy in 1.8 Gy fraction (BED for early effects will be 45 Gy, assuming  $\alpha/\beta$  of 10; BED for late effects will be 72.5 Gy, assuming a  $\alpha/\beta$  of 3).

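### Do the BED figures for dose level IV in section 1.3, which do not reproduce, call for a change to the plan?

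*Combined protocol and SAP*

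**What the plan says.** Section 1.3 closes by describing the top dose level, 35 Gy in 10 twice-daily fractions of 3.5 Gy. It states that this schedule "has a Biological Effective Dose (BED) equivalent of the standard fractionation of 45 Gy in 1.8 Gy fraction". In parentheses it adds "BED for early effects will be 45 Gy, assuming" an α/β of 10, and "BED for late effects will be 72.5 Gy, assuming a" α/β of 3. No formula is named.

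Earlier in the same section, models from the partial-breast literature are reported as showing that a "regimen of 38.5 Gy in 10 fractions should provide a biologically equivalent dose (BED) of 45 Gy in 1.8 Gy fractions", also at α/β 10. The pilot study behind that statement used 34 Gy and 38.5 Gy, "both delivered in 10 fractions, twice daily over 5 consecutive days". The section also cites "MammoSite HDR brachytherapy (34 Gy, 3.4 Gy fraction, in 10 fractions", and another series that used a "total dose of 30 Gy at 6 Gy/fraction delivered in 5 fractions over ten days".

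The treatment plan (section 4.2.5) defines the level in physical dose only: "Dose level IV: 35 Gy total (3.5 Gy for 10 fractions".

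**The concern.** Two different 10-fraction doses, 38.5 Gy and 35 Gy, are each said to match 45 Gy in 1.8 Gy fractions. Besides that, the two BED values printed for level IV do not follow from its own fraction size. These are the only biological-dose figures given for any tested level of a dose-finding trial. If the top level had been admitted to the design on the strength of that equivalence, or if any rule used BED, an error here could affect which doses are tested or how their toxicity is judged.

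**Working it through.** **Inputs.** All come from section 1.3, with level IV cross-checked against section 4.2.5: level IV = 10 × 3.5 Gy; comparator = 45 Gy in 1.8 Gy fractions, so 45/1.8 = 25 fractions; other cited schedules = 10 × 3.85, 10 × 3.4 and 5 × 6 Gy; α/β = 10 (early) and 3 (late).

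**Formula.** BED = n·d·(1 + d/(α/β)), with no term for overall time or incomplete repair. The documents do not name it, so it is first tested on a statement they make.

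**Step 1: reproduce the document's own equivalence (α/β 10).**
- 38.5 Gy in 10: 38.5 × 1.385 = 53.32 Gy.
- 45 Gy in 25: 45 × 1.18 = 53.10 Gy.

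These agree to 0.4%, so this formula fits the 38.5 Gy statement.

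**Step 2: level IV.**
- α/β 10: 35 × 1.35 = 47.25 Gy; printed 45. 45/47.25 − 1 = −4.8%.
- α/β 3: 35 × 2.1667 = 75.83 Gy; printed 72.5. 72.5/75.83 − 1 = −4.4%.

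**Step 3: compare schedules.**

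| Schedule | BED, α/β 10 | BED, α/β 3 |
|---|---|---|
| 10 × 3.4 Gy | 45.56 | 72.53 |
| 10 × 3.5 Gy (level IV) | 47.25 | 75.83 |
| 5 × 6 Gy | 48.00 | 90.00 |
| 10 × 3.85 Gy | 53.32 | 87.91 |
| 25 × 1.8 Gy (comparator) | 53.10 | 72.00 |

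Level IV against the comparator: 47.25/53.10 − 1 = −11.0% (early) and 75.83/72.00 − 1 = +5.3% (late). Equality requires 35 + 122.5/x = 45 + 81/x, so x = 41.5/10 = 4.15, which is neither stated α/β. As an equivalent dose in 1.8 Gy fractions, level IV is 47.25/1.18 = 40.0 Gy (early) and 75.83/1.6 = 47.4 Gy (late).

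**Step 4: could another model rescue the sentence?**
- *Time term* (assumed: courses of 5 and 33 days, constant daily loss, α/β 10). Equality needs (53.10 − 47.25)/28 = 0.21 Gy/day, but level IV is then 47.25 − 5 × 0.21 = 46.2 Gy, not 45. Printing 45 needs 2.25/5 = 0.45 Gy/day, which puts the comparator at 53.10 − 33 × 0.45 = 38.25 Gy.
- *Incomplete repair* (assumed half-times of 0.5 to 4 h, 4 h gap). Level IV at α/β 10 ranges from 47.3 to 53.4 Gy. A half-time near 3.75 h reaches 53.1 Gy, but moves further from the printed 45 and, at α/β 3, further from equality.

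So equivalence at α/β 10 depends on the model. Neither alternative recovers the printed early value together with the equivalence. The gap between 38.5 and 35 Gy in 10 fractions is 53.32 − 47.25 = 6.07 Gy. A time term barely alters it: even if the trial course spans a weekend, two extra days at 0.21 Gy/day are about 0.4 Gy.

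**Step 5: where does BED enter the plan?**
- Sections 4.2.1 and 4.2.5 (dose levels, escalation, MTD): total dose, fraction size and counts of DLT in up to 6 patients.
- Section 4.2.6 (DLT): toxicity grades, necrosis and treatment interruption.
- Section 4.2.7 (expansion): safety in 18 patients.
- Section 10.1 (operating characteristics): DLT rates only. At a true rate of 20%, P(0 or 1 of 6) = 0.8⁶ + 6(0.2)(0.8⁵) = 0.262 + 0.393 = 0.655, the stated 66%. At 35%, 1 − 0.65⁶ − 6(0.35)(0.65⁵) = 1 − 0.075 − 0.244 = 0.681, the stated 68%.
- Section 10.3.2 (stopping): counts of radiation-related toxicity.

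None of these uses a BED.

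**The case for a change.** The best case for acting runs as follows. The sentence is the only stated biological rationale for the top level. The late-effect slip hides a difference, since the printed 72.5 Gy looks level with the comparator's 72.0 Gy while the computed value is 75.83 Gy. Sections 6.2.1 and 6.3.1 list skin fibrosis as a risk, and the DLT window closes 30 days after radiation, so late effects are where a reader might lean on the background. Correcting the text would cost almost nothing.

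The arithmetic in that case stands, and so does the contradiction within section 1.3. The consequence does not. The risk descriptions in section 6 are qualitative and cite no BED. On recomputation, level IV still lies between the 34 Gy and 38.5 Gy schedules cited in the same section, at both α/β values (45.56 to 53.32 Gy and 72.53 to 87.91 Gy), so the cited experience brackets it with or without the equivalence. Level IV opens only after 6 patients at each of levels II and III with at most one DLT, so observed toxicity governs entry. Nor do the corrected figures point one way: early BED falls below the comparator and late BED rises above it.

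**Conclusion.** This is a slip in background text and calls for no change to the plan. Under the linear-quadratic formula without time or repair terms, the printed BEDs for level IV are 4.8% low (45 against 47.25 Gy) and 4.4% low (72.5 against 75.83 Gy). The equivalence to 45 Gy in 1.8 Gy fractions misses by −11.0% for early and +5.3% for late effects. It also cannot stand beside the same claim for 38.5 Gy in 10 fractions. The two statements in section 1.3 contradict each other and must be reconciled as text, but that is an editorial matter. This rests on the α/β values the protocol assumes, and on the fit of the formula to the protocol's own 38.5 Gy statement. The documents do not show how the printed pair arose. Whatever the corrected wording, the dose levels, patient numbers, decision rules and analyses stay as written, and so does what the trial can conclude. No view is taken on any dose or schedule.
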